- 1. To assess the safety and efficacy of the current FDA-approved 1 mg b.i.d. varenicline for smoking cessation in comparison with placebo when used in a simulated OTC study with no behavioral support provided.
- 2. To assess the safety and efficacy of .5mg b.i.d. varenicline in comparison with 1mg b.i.d. varenicline and placebo when used in a simulated OTC study with no behavioral support provided.

Secondary Objectives

- 1. To evaluate whether subject specific characteristics (e.g. socioeconomic status, ethnicity, smoking history, etc.) moderate primary (safety and efficacy) and secondary (adherence) outcomes.
- 2. To evaluate medication use patterns to assess whether varenicline is being used as indicated on the label, and to determine if medication adherence mediates cessation outcomes between-subjects.

3. In a subsample of participants, to examine how medication adherence, withdrawal, and side effects (e.g. nausea and sleep disturbance) vary within-subjects and are associated with smoking status using EMA in the first two critical weeks of medication use.

[figure not shown]
Hypotheses

- 1. Quit rates in the 1 mg b.i.d. varenicline condition will be significantly higher than the placebo medication condition when provided as an OTC medication.
- 2. Quit rates in the .5 mg b.i.d. varenicline condition will be comparable to the 1mg b.i.d. varenicline condition, and will be significantly higher than the placebo medication condition, when provided as an OTC medication.
- 3. Side effects will show a dose response relationship, with effects lowest in the placebo group.

C. EXPERIMENTAL METHODS Study Design

The primary objective of this study is to assess the efficacy of two different doses of varenicline used in a simulated OTC intervention relative to placebo (total N = 432). The design is a three-group placebo-controlled, double blind, block randomized clinical trial (as indicated in the figure), where participants will be randomly assigned to one of three

conditions: (1) 1 mg b.i.d. varenicline for 12 weeks, which is the current FDA-approved dose, (2) 0.5 mg b.i.d. varenicline for 12 weeks, or (3) placebo.

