- 6. Literate in English, self-report
- 7. Must be available for the duration of study
- 8. Informed consent obtained
- 10. Must own study compatible smart-phone (iPhone or Android)
- 11. Must be a current resident of the United States

Exclusion Criteria for the Remote Cohort

1. Any self-report, diagnosis or treatment of heart attack, unstable angina, angioedema, seizures, cerebrovascular accident (CVA) within the last six months.

- 2. Any self-report, diagnosis or treatment of bipolar, schizophrenia or suicidal ideation within the last six months. (For suicidal ideation a score of ≥7 on the Suicidal Behavior Questionnaire, see Appendix 15)
- 3. Self-report of diagnosis or treatment for depression within the past six months, unless participant has written permission by their healthcare provider to participate
- 4. History of renal disease
- 5. Allergy to any of the ingredients in varenicline
- 6. Participation in another smoking cessation program or any type of clinical trial in the past 3 months
- 7. Use of any smoking cessation medication in the past three months
- 8. Any other medical condition(s) which the licensed study physician deems unacceptable for participation in this study
- 9. Consume greater than 21 alcohol drinks per week.
- 10. No two members of the same household may participate in this study
- 11. No study staff or their immediate family may participate in the study
- 12. Females who are pregnant, breast feeding, or not currently using a medically approved form of birth control and unwilling to do so.

 Acceptable methods of birth control include abstinence, oral contraceptives, the contraceptive patch, the contraceptive ring, and condoms.

Behavioral Support

No behavioral support will be provided by the study team at any visit. At all follow-up visits post-randomization, they will not be given encouragement by study staff to quit smoking, nor be provided with any information or instruction about medication usage other than consent form and Chantix Use and Safety Information handout (see Appendix 12). We will assess at each visit whether subjects used any behavioral support available in the community.

Risk/Benefit Assessment

Risk Category. Greater than minimal risk

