participants no more than 90 seconds to complete. To reduce missing data, participants who miss more than two sequential days of evening daily diaries or complete fewer than three scheduled prompts a day for two sequential days will receive encouragement texts and calls from an RA to troubleshoot any problems with the app and encourage compliance.

Definitions of Success

FDA Abstinence Criteria. As indicated earlier, in all studies that assess medications for smoking cessation, the FDA typically requires verification of 28 days of continuous abstinence, i.e.; not a single puff from a single cigarette. The FDA does not require the 'clock' to start at a consistent time point after study enrollment. Thus, in many studies the 'clock' on that 28 days begins two weeks after study medication has begun, while in other studies the 'clock' starts at a different time point. In the current study, we will follow the protocol used in the varenicline pivotal trials. ^{6,17-20} The primary study outcome in the proposed study will be continuous abstinence between weeks 8 and 12 after study medication has begun. Subjects who are randomized but who never obtain medication will be considered treatment failures and will be included in the denominator in the intent-to-treat analyses.

D. DATA SAFETY MONITORING PLAN

Participant Safety. This study includes the use of a medication, varenicline, that is FDA-approved, as well as the same medication at a lower dose than approved by the FDA, in order to assess whether smokers can choose and use the medication without a healthcare provider prescription. Given the existing data, the likelihood of participants experiencing a serious adverse event from the use of varenicline is very low. In fact, in one of the largest smoking cessation studies ever conducted, the adverse events related to varenicline were similar to those from the nicotine patch, which is already approved as an OTC medication.

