Sample Size. The primary analysis of this study is to compare the quit rates between groups. The sample size estimation is based on the results from Oncken et al.⁶ the quit rates at 12 weeks for 0.5, 1.0 mg b.i.d. titrated groups and control group are approximately 45%, 60% and 15%. In an OTC setting, we assume the rates would reduce by half. Therefore, 23%, 30% and 8% are used to determine the sample size. Since we are interested in comparing the two active treatment arms with the control arm, to control for the overall type I error rate, the Bonferroni adjustment is applied: for each comparison, the type I error is 0.025. With 110 participants per group, we have at least 80% power to detect a difference of 23% vs. 8% (0.5mg vs. control) by the chi-square test. Even though a smaller sample size is required to detect a difference of 30% vs. 8% (1.0mg b.i.d. vs. control), we plan to enroll equal number of participants for each arm.

For the EMA component of the study, we anticipate the primary outcomes for each treatment condition in the EMA subgroup will not be statistically different from the non-EMA sample and plan to analyze the primary outcomes based on the combined sample. However, the data collected will provide information to quantify the longitudinal within subject association. In particular, we hypothesize that the severity of side effect will increase in the first 5 days after the initiation of treatment, and expect the odds of side effect at day 5 is three times the odds at day 1. Based on our simulations (type I error 0.05, 5 time points, and intra-class correlation 0.3), with 25 participants per group, we have at least 80% power to detect an odds ratio of 3.

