Data Sharing Plan. The information that we will collect includes medically-related information that is protected and must remain confidential, so all standard methods to protect participant confidentiality will be employed, including maintaining information in password protected encrypted databases to reduce the risk of a data breach. Shared data across the two study sites will likewise be password protected and encrypted. After study completion, any outside requests for data will require a data sharing agreement that assures the following: (1) all data must be maintained in a secure fashion using appropriate technology, (2) commitment to use the data only for the research purposes requested, and (3) all shared data must either be destroyed or returned, including written assurances to that effect.

Statistical Analysis Plan

Main study. The participation flow will be reported following CONSORT guidelines. Intention to treat analysis will be applied for all statistical analyses. The data collected from the study will be summarized by the descriptive statistics for overall and by treatment condiction (1mg b.i.d., .5mg b.i.d. and placebo) and by the application of EMA (yes/no). The primary analysis will include estimating and comparing the guit rates between treatment arms. We will fit a logistic regression to model the probability of smoking cessation at 12 weeks with treatment condition, application of EMA and the interaction term of the two main effects as independent variables. If the interaction term is not significant, this implies the guit rates for the same treatment condition are similar in those with and without the utilization of EMA, and we will drop the interaction term and fit a model with main effects only. The comparison will be perfromed by the Wald test from the logistic regression with Bonferroni adjustment to account for multiple comparisons. The point estimate of guit rate and 95% confidence interval (CI) for each treatment condition will be reported. If the interaction term is significant, we will conduct the comparisons in EMA and non-EMA subgroups. A similar approach will be applied to the analysis of adherence and adverse events. These two outcome variables can be analyzed as a dichotomous (yes/no) or count variable (pill count and number of adverse events), and the logistic regression and Poisson regression will be used to evaluate whether group differences occur. In the secondary analysis, to evaluate

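### A non-significant treatment-by-EMA interaction does not show that quit rates are similar with and without EMA; the EMA coefficient with its interval answers that question

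*Combined protocol and SAP*

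**What the plan says.** Section E, Statistical Analysis Plan, Main study, models quitting at 12 weeks by logistic regression on treatment, EMA participation and their interaction. On the outcome of the interaction test it says: "If the interaction term is not significant, this implies the guit rates for the same treatment condition are similar in those with and without the" use of EMA. The interaction is then dropped and a main-effects model fitted, with EMA still in it. Arms are compared by Wald tests with a Bonferroni adjustment, and a quit rate with 95% CI is reported per arm. Only a significant interaction leads to separate EMA and non-EMA comparisons. A similar approach is to be used for adherence and adverse events. Descriptive summaries by EMA status are also planned.

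No level is given for the interaction test. No test, estimate or interval is named for the EMA coefficient.

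Section E, Sample Size, states an expectation, "we anticipate the primary outcomes for each treatment condition in the EMA subgroup will not be statistically different from the non-EMA sample", and plans to analyze the combined sample.

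The EMA Sub-Study (Section C) randomly assigns 25 people per condition to two weeks of scheduled prompts and an evening diary. Those who miss entries "will receive encouragement texts and calls from an RA to troubleshoot any problems with the app and encourage compliance". For the trial as a whole, Behavioral Support (Section C) says: "No behavioral support will be provided by the study team at any visit".

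**The concern.** The sentence is about quit rates within one treatment condition, with EMA against without. The term it relies on compares the EMA effect across conditions. These are different hypotheses: if EMA moved quitting equally in every arm, the interaction would be zero and the sentence would still be false. The term that bears on the sentence is the EMA coefficient, which the plan fits in the next step and then leaves unreported.

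The trial asks what varenicline achieves without behavioral support. EMA participants have extra daily contact and self-monitoring that other participants do not. If that contact affected quitting, a same-direction shift in all arms is one obvious pattern, and it is the one this test is not built to see. At stake are the statement that EMA made no difference and, to a lesser degree, the reading of each arm's rate as a quit rate without support.

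**Working it through.** **Inputs from the documents**
- Quit rates (Section E, Sample Size): "Therefore, 23%, 30% and 8% are used to determine the sample size", for 0.5 mg, 1 mg and placebo. They are used here as the non-EMA rates, in the order placebo / 0.5 mg / 1 mg.
- Level for each active-versus-placebo comparison (same section): "for each comparison, the type I error is 0.025".
- 432 randomized 1:1:1, so 144 per arm. With 25 in EMA, 119 per arm are not.

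**Assumptions (not in the documents)**
- Interaction test with 2 df at two-sided 0.05.
- Cohorts pooled.
- An EMA effect on quitting: a common odds ratio of 1.5 to 3, or an equal rise in points in every arm.

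**1. The plan's own figure.** Sample Size gives at least 80% power for 23% vs. 8% with 110 per group. With mean rate 0.155, power = Φ[(0.15·√110 − 2.241·√(2·0.155·0.845)) / √(0.23·0.77 + 0.08·0.92)] = Φ[(1.573 − 1.147)/0.501] = Φ(0.851) = 80.3%. The figure is reproduced with a two-sided 0.025. The plan states no power for the interaction test or the EMA effect.

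**2. The logic.** Write logit(p) = α_t + β·EMA + γ_t·EMA for arm t, with γ = 0 in the reference arm. The interaction null is γ_t = 0 in every arm. Equal quit rates with and without EMA in arm t require β + γ_t = 0. The first condition does not constrain β. Example with β = log 3: 8% is odds 0.087, tripled 0.261, which is 20.7%. In the same way 23% becomes 47% and 30% becomes 56%. The interaction is exactly zero, and the average rate is 41% with EMA against 20% without. A larger sample would not help.

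**3. How often each test rejects.** Simulation of the plan's models, 119 non-EMA and 25 EMA per arm. The two interaction figures are Wald / likelihood ratio.

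| EMA effect in every arm | EMA quit rates (%) | Interaction rejects (%) | EMA coefficient significant (%) |
|---|---|---|---|
| OR 1.5 | 12 / 31 / 39 | about 4 / 6 | about 27 |
| OR 2 | 15 / 37 / 46 | 3.7 / 6.0 | about 66 |
| OR 3 | 21 / 47 / 56 | 4.0 / 5.5 | about 97 |
| +10 points | 18 / 33 / 40 | 7.9 / 8.9 | about 48 |
| +15 points | 23 / 38 / 45 | 10.5 / 11.3 | about 80 |

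For a common odds ratio the interaction test rejects at about its own size. For equal rises in points it does a little better, reaching about 15% at +25 points. With 110 per arm (85 non-EMA) the results are nearly the same.

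**4. Shift in the reported arm rates.** Shift = 25/144 × (EMA rate − non-EMA rate).
- OR 1.5: 0.6 / 1.4 / 1.6 points
- OR 2: 1.2 / 2.5 / 2.8 points
- OR 3: 2.2 / 4.2 / 4.6 points

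For comparison, the 95% CI half-width 1.96·√(p(1−p)/144) is 4.4 / 6.9 / 7.5 points.

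**5. What the data could say about EMA.** With no EMA effect, the mean of p(1−p) over arms is (0.0736 + 0.1771 + 0.2100)/3 = 0.1536. SE = √[0.1536 × (1/75 + 1/357)] = 0.050, so the 95% CI half-width is about 10 points. On the odds-ratio scale the SE of the log is about 0.33, giving an interval of roughly 0.53 to 1.9. Even the right term could not establish close similarity.

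**6. Who can be in EMA.** The sub-study instruction step is in the in-person Screening/Baseline list and not in the remote one. Willingness to do EMA is in-person inclusion criterion 9; the remote list jumps from 8 to 10. If EMA is in-person only, a 75-versus-357 contrast sets EMA participants partly against remote participants, whose abstinence is verified by urine cotinine instead of breath CO. It would not be a purely randomized contrast.

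**The case against.** Little rests on the clause. The primary question is active against placebo, EMA is randomly assigned within each condition, and it stays in the main-effects model. A reader might infer that the efficacy comparisons are biased or that the wrong branch harms them. The documents do not support that: a uniform EMA effect is adjusted for. This part of the objection stands in full.

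A reader might also infer that a large EMA effect would be hidden. Descriptive summaries by EMA status are planned, so it could be seen there. The plan says that non-significance implies similarity; it does not order a formal similarity result. The inference is still wrong, and no interval is attached to the quantity concerned.

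The assumed effects have no source in the documents. EMA lasts two weeks, while the primary outcome is abstinence in weeks 8 to 12. The staff calls concern compliance with EMA entries and go only to those who miss them, so they should not be read as quit support or as a breach of the Behavioral Support rule. This stands: the effect sizes are illustrations and small ones must be shown too. The gap between the two tests is only about 20 to 25 points at OR 1.5 and about 40 at +10 points, against about 60 at OR 2 and over 90 at OR 3.

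Finally, the Sample Size sentence on EMA says what the authors anticipate. It does not claim that the groups have been shown to be alike, and it needs no change.

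**Conclusion.** The inference in the Main study paragraph is wrong as written, on logic alone. The numbers show that it matters in practice: under a common EMA odds ratio of 2 or 3, the interaction would be non-significant in about 94 to 96% of trials, and similarity would be inferred each time.

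The reach is limited. Treatment-versus-placebo comparisons are unaffected. What is affected is the similarity conclusion and the arm-level quit rates, which move by about 0.6 to 4.6 points for odds ratios of 1.5 to 3, less than the plan-rate interval half-widths. If the in-person cohort is analyzed alone, as Analysis of the Remote Cohort plans first, and EMA is confined to it, EMA's share exceeds 25/144 and the shift is proportionately larger; the documents do not give the cohort split. All these sizes rest on the assumed EMA effects, the 0.05 interaction level and pooled cohorts. The logical point rests on none of them.

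**What to change.** In Section E, Statistical Analysis Plan, Main study:
- Delete the clause that infers similar quit rates from a non-significant interaction.
- State instead that the effect of EMA on quitting will be estimated by the EMA coefficient in the main-effects model, reported as an odds ratio and a quit-rate difference with 95% CI, and that similarity will not be concluded from a non-significant interaction. Carry the same wording over to adherence and adverse events, where a similar approach is planned.
- State whether EMA is offered only to the in-person cohort. If so, estimate its effect within that cohort, or include a cohort term in any combined model.
- Report the model-based quit rate and 95% CI per arm at EMA = no as a supplementary line beside the planned combined rates. The combined rates remain the plan's main report.

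The cost is a wording change and a few lines of output from a model already planned, with no new data or participants. The downside is that the EMA difference will carry an interval of about ±10 points, wider if only in-person participants contribute, so the report cannot claim that EMA and non-EMA participants quit at similar rates.

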- Minnesota Nicotine Withdrawal Scale (MNWS, see Appendix 4). This brief staff or subject administered form will assess cigarette-related craving and withdrawal.
- Medical History—Pertinent medical history will be assessed and documented on the Medical History CRF by the study coordinator through a review of systems, allergies, and recent surgeries
- Previous and Concomitant Medications. Medications taken within the previous 30 days of the Screening/Baseline visit will be documented in the Concomitant Medication CRF
- Body weight and height-height in meters (to the nearest cm) and weight in kilograms (to the nearest 0.1 kg in light indoor clothing and without shoes will be measured.
- Vital signs including blood pressure and heart rate, measured after the subject has been seated and resting for at least 5 minutes.
- Fagerström Test of Cigarette Dependence (FTCD, see Appendix 7). This 5 item subject completed questionnaire measures dependence on cigarettes.
- Urine pregnancy test for all females
- Urine drug screen. The urine test for drugs of abuse (eg opiates, amphetamines, benzodiazepines, cocaine or other substances) will be performed only at the Screening/Baseline Visit. Subjects who test positive will be excluded, unless they can provide the clinic with a copy of a current prescription for opioids or stimulants.
- A portion of this urine will be stored for exploratory analysis of nicotine and nicotine metabolism that might be related to treatment outcomes, only at the ASU site.
- Breath Carbon Monoxide test. The breath CO will be collected after a 15 second breath hold using the Bedfont Micro Plus (Bedfont Inc).

- If the subject requires study approval from their own physician, the Investigational Product will be dispensed upon their return to the clinic with the signed authorization (Appendix 8)
- If subject meets all inclusion and exclusion criterion, a study ID will be assigned and he/she will be randomized in a 1:1:1 fashion to 1.0 mg b.i.d. varenicline, .5mg b.i.d. varenicline, or placebo. Participants and study staff will be blinded to the assignment.
- Investigational Product educational information will be provided to participants
- The first five weeks of Investigational Product dispensed
- If randomized into the substudy, subjects will be instructed on how to respond to the text messages
- Suicidal Behavior Questionnaire (Appendix 15)

Week 2 Visit for the In-person Cohort

- Telephone call
- Minnesota Nicotine Withdrawal Scale

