Methods. We will randomly assign 25 people from each condition to participate in the EMA sub-study that lasts two weeks after the participants begin using varenicline, and they will be informed in the consent form at the Baseline/Screening visit that they may be asked to participate in the sub-study. We will use two types of EMA data assessments: (1) evening daily diaries to collect information on concrete behaviors (e.g., smoking and taking medication) that occurred that day, and (2) scheduled prompts to assess states (e.g. mood, craving, nausea) that fluctuate throughout the day (Appendix 13). Data will be collected using scheduled text messages linked to Qualtrics, which provides HIPPA-compliant data collection. At the Baseline/Screening visit, the research assistant will enroll substudy participants in the text message EMA data collection and will train participants how to respond to the scheduled prompts and the daily diary EMA surveys. The evening daily diary will include two brief questions on cigarette and varenicline pill consumption that day. In addition to the daily diary, participants will also respond to up to five scheduled prompts throughout the day. The first scheduled prompt will occur at 9am, and will include five brief questions on vivid dreaming and sleep quality from the last night, momentary nausea, momentary mood, and momentary craving. After the first scheduled prompt of the day is completed, subsequent scheduled prompts will ask about momentary nausea, mood, and craving only. Participants will be prompted to complete scheduled surveys at waking and at every four hours. Scheduled prompts will expire 30 minutes after their scheduled time; evening daily diaries can be completed any time after their scheduled time until midnight.

EMA Data Collection Summary. Table 3 shows the information and frequency that will be collected via EMA.

Table 3. EMA schedule of assessments.

	Baseline	Week	
		1	2
Assignment to EMA sub study	Χ		
Subject review of Varenicline Label	X		
Text message instructions	X		
Scheduled prompts			
Vivid dreaming (last night)		X	Х
Sleep quality (last night)		X	Х
Nausea (current)		X	Х
Mood (current)		X	Х
Cigarette craving (current)		X	Х
Daily diaries			
Number of cigarettes smoked that		Х	Х
day		^	
Varenicline taken that day		X	X
Additional thoughts/feelings?		X	Χ

EMA compliance and feasibility. The EMA scheduled prompts and daily diary are extremely brief. Similar assessments from [name] Study took typical

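### A treatment-by-EMA interaction test can replace the overall primary comparison with subgroup comparisons that have no overall test, no alpha split and no deciding result

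*Combined protocol and SAP*

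**What the plan says.** Section E, Statistical Analysis Plan, Main study, models cessation at 12 weeks by logistic regression on treatment, EMA participation and their interaction. If the interaction is not significant, it is dropped and the arms are compared by Bonferroni-adjusted Wald tests from the main-effects model. Otherwise: "If the interaction term is significant, we will conduct the comparisons in EMA and non-EMA subgroups". The same section applies a similar approach to adherence and adverse events.

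Other sections bear on this:

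- Section E, Sample Size, expects no difference between EMA and non-EMA participants on the primary outcomes, and the investigators "plan to analyze the primary outcomes based on the combined sample".
- The same section sets the error rate ("for each comparison, the type I error is 0.025") and powers only the overall comparison.
- EMA Sub-Study, Methods: "We will randomly assign 25 people from each condition to participate in the EMA sub-study".
- Section B, Hypotheses, compares treatment conditions with no reference to EMA.

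**The concern.** The primary hypotheses have one natural test: each active arm against placebo among everyone randomised. The SAP makes that test conditional on a preliminary significance test. When the preliminary test is significant, the powered comparison disappears and up to four comparisons take its place (two doses in two subgroups). For that branch the plan does not say:

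- at what level, or by what test, the interaction is judged;
- whether 0.025 is divided further over the four tests (a Bonferroni adjustment is mentioned in general, without a divisor for this case);
- whether success needs both subgroups, either one, or a particular one.

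EMA participation is an assessment sub-study assigned at random, and the investigators expect it not to affect the primary outcomes. On that expectation, a significant interaction is a false positive. The trial could then report one positive and one null subgroup for the same dose, with no pre-specified overall answer.

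**Working it through.** **Inputs.** Planning rates: "23%, 30% and 8% are used to determine the sample size" (0.5 mg, 1.0 mg, control). Error rate 0.025 per comparison, taken as two-sided because that reproduces the stated sample size. Study Design: "relative to placebo (total N = 432". Screening/Baseline: "randomized in a 1:1:1 fashion to 1.0 mg b.i.d. varenicline, .5mg b.i.d. varenicline, or placebo", so 432/3 = 144 per arm. EMA: 25 per arm, leaving 144 − 25 = 119 per arm without EMA.

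**Step 1: the plan's own figure.** Sample Size states: "With 110 participants per group, we have at least 80% power to detect a difference of 23% vs. 8" per cent. With pooled variance under the null,

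n = [z(1−α/2)·√(2p̄(1−p̄)) + z(1−β)·√(p₁(1−p₁)+p₂(1−p₂))]² / (p₁−p₂)²

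Here p̄ = 0.155, √(2 × 0.155 × 0.845) = 0.5118 and √(0.1771 + 0.0736) = 0.5007. So

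n = (2.2414 × 0.5118 + 0.8416 × 0.5007)² / 0.15² = 109.4, rounded up to 110, with power 80.3%.

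The stated figure reproduces.

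**Step 2: marginal power in each analysis set.** Power = Φ[(|p₁−p₂|·√n − 2.2414·√(2p̄(1−p̄))) / √(p₁(1−p₁)+p₂(1−p₂))]. For 23% vs 8% at n = 25 this is Φ[(0.75 − 1.1472)/0.5007] = Φ(−0.793) = 21.4%.

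| Analysis set | n per arm | 23% vs 8% | 30% vs 8% |
|---|---|---|---|
| Overall, 432 randomised | 144 | 90.4% | 99.6% |
| Non-EMA | 119 | 83.6% | 98.5% |
| EMA | 25 | 21.4% | 39.4% |

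If only the powered 110 per arm were reached, the non-EMA subgroup would have 85 per arm and 68.1% power for 23% vs 8%. If the four tests shared 0.05 (0.0125 each), power for 23% vs 8% would be 76.3% (non-EMA, 119 per arm) and 14.6% (EMA).

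The EMA figure is generous. About 25 × 0.08 = 2 placebo quitters are expected, and none occurs with probability 0.92²⁵ = 12.4%. With the Wald test that the plan names for treatment comparisons, simulated EMA power is about 4% (0.5 mg) and 16% (1.0 mg).

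**Step 3: how often chance opens the gate.** The interaction has (3−1)(2−1) = 2 degrees of freedom. Simulations used 40,000 trials per scenario, 119 + 25 per arm, no true interaction and an assumed 0.05 level. The Wald test counts as non-significant where an empty cell prevents its calculation.

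| Quit rates | Likelihood-ratio test | Wald test |
|---|---|---|
| Planning rates | 6.3% | 2.6% |
| 8% in all arms | 7.4% | 0.5% |
| 20% in all arms | 6.2% | 2.9% |

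**Step 4: what happens once it opens.** A significant interaction selects trials in which the subgroups look different, so the Step 2 powers do not apply there. At the planning rates with the likelihood-ratio gate and chi-square subgroup tests, 0.5 mg is significant in about 79% of opened trials in the non-EMA subgroup and 41% in the EMA subgroup. The two verdicts disagree in about 69%. The set-aside overall test is significant in about 91% of the same trials.

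**Step 5: effect over all trials** (Wald comparisons at 0.025, 144 per arm).

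- Power for 0.5 mg is 91.0% with the overall test always primary. If success in an opened trial needs both subgroups, it is 85.6% (likelihood-ratio gate) or 88.8% (Wald gate). If either subgroup suffices, it is 90.3–91.0%.
- If any of the four tests at 0.025 counts, familywise error moves from 4.5% to 5.5–5.8% at a common 20% quit rate, and from 3.4% to 3.5–3.8% at a common 8%.

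**The case against.** The case for leaving the text alone has several parts.

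- **The gate rarely opens, and the larger subgroup is well sized.** A reader might infer that the trial would be reduced to 25 per arm, or that a significant interaction is to be expected by chance. The documents support neither. Only the EMA subgroup has 25 per arm; the non-EMA subgroup's marginal power (84%) exceeds the planned 80%. In every scenario run, the gate stays shut in more than 92% of trials.
- **The error rate is not seriously inflated.** A reader might take 1 − (1 − 0.025)⁴ = 9.6% as the trial's familywise error. That would be the nominal rate for four independent tests always performed. They are performed only when the gate opens, and Step 5 gives at most 5.8% in the scenarios run.
- **There is a reason to check for an EMA effect.** The trial tests treatment without behavioural support, yet EMA participants monitor themselves repeatedly and receive reminder contacts if their compliance drops. Willingness to do EMA is an inclusion criterion only for the in-person cohort. If EMA is confined to that cohort, which the documents do not say outright, EMA and cohort are partly confounded in pooled data.
- **Sample Size is not a flat contradiction.** It states an expectation and a default, and the SAP follows that default unless the interaction is significant.

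These points limit the size of the problem and justify reporting the interaction. They do not supply the missing overall test, alpha split or deciding result.

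**Conclusion.** The point holds, at moderate weight. On one of its two pre-specified paths the plan has no defined primary answer, and that path is chosen by a test whose method and level are not given. Following the rule as written would usually produce conflicting subgroup verdicts on 0.5 mg (about 69% of opened trials, likelihood-ratio gate) although the overall test would be significant in about 91% of them.

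The path is uncommon: about 6–7% of trials by likelihood-ratio test and about 3% by Wald test at the planning rates. The worst reading examined costs 91.0 − 85.6 = 5.4 percentage points of power for 0.5 mg. This is a defect in how the primary analysis is defined. It does not show that the trial is underpowered or that its overall error rate is seriously inflated.

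The figures assume two-sided tests, a 0.05 interaction level, 144 per arm, no true interaction, and the in-person and remote cohorts pooled. The section on the remote cohort plans separate cohort analyses first, which would make the subgroups smaller.

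**What to change.** In the Main study section of the SAP:

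1. Make the overall treatment comparison from the main-effects model already in the plan (treatment and EMA), at 0.025 for each active-versus-placebo comparison, the primary analysis whatever the interaction shows.
2. Report the treatment-by-EMA interaction, with its test and level named, and the EMA and non-EMA estimates with confidence intervals, as sensitivity analyses.
3. Apply the same rule to adherence and adverse events, which now inherit the two-step approach.

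The cost is a wording change, with no extra data or participants and no new model terms. The one downside is that if EMA truly modifies the treatment effect, this will appear only as a secondary result.
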